6.9 Study Visit Procedures

Visits will occur annually for a total of 4 years following the below schedule with visit windows of +/- 1 month.

	Visit 1	Visit 2	Visit 3	Visit 4
Cohort 1	72 Months	84 Months	96 Months	108 Months
Cohort 2	36 Months	48 Months	60 Months	72 Months

The following study procedures will be completed only at Visit 1:

- If the participant agrees to continue in the Extension study, the Principal Investigator or appropriate designee will obtain the participant's consent
- Eligibility Criteria Review
- Demographics and Participant Contact Information Review
- Medical/Ophthalmic History Review (carried over from NTMT-01 or NTMT-02 study, including any AE's that have occurred since the last participant visit)

The following study procedures will be completed bilaterally at all visits for all participants unless otherwise noted:

- Adverse Event Assessment (only at Visits 2, 3, and 4)
- Concomitant Medications
- Manifest refraction
- Best Corrected Visual Acuity
- Goldmann applanation tonometry
- Microperimetry
- Slit lamp biomicroscopy

- Dilated fundus examination
- Implant site clinical examination
- SD-OCT
- Fundus Autofluorescence imaging
- Digital Color Fundus photographs
- Reading Speed – (Cohort 2 participants only)
- Adaptive Optics Scanning Laser Ophthalmoscopy (AOSLO), in selected participants

Participants who underwent AOSLO for NTMT-02 will undergo a separate consent process at the AOSLO Center if they agree to continue participating

7 Monitoring Participants and Criteria for Withdrawal

7.1 Safety Plan

A Safety Plan will describe roles and responsibilities, adverse event reporting methods and requirements, communication and interaction with the Data and Safety Monitoring Committee (DSMC), grading the severity of adverse events and other safety monitoring processes. The plan will be based on the safety reporting requirements for investigational new drug applications (INDs) found in 21 CFR part 312 and other applicable regulatory authorities' regulations.

7.2 Adverse Experience Reporting

All adverse events (AEs) either observed by the Investigator or one of his/her medical collaborators, or reported by the participant spontaneously or in response to direct questioning, will be reported. Any adverse event regardless of severity or potential association with the device or CNTF or study procedures must be documented in study records by the Investigator and appropriately reported.

AEs will be reported within the participant's records and in the AdvantageEDCSM system. All AEs should be entered into the data system within 5 business days of identification by the site personnel. All AEs will be recorded from the date of obtaining informed consent until the last study visit.

Serious adverse events (SAEs) will be followed until resolution or until stability is reached. In rare instances, this may include following the participant after completion of the study.

All serious adverse events should be entered into the data system within 24 hours of identification. If there are technical difficulties when entering the event into the EDC system, the

SAE will be reported to the Coordinating Center by fax communication, and these numbers will be provided in the Manual of Operations. All information reported by fax will need to be entered in the data system when it is available. All SAEs should be reported to local Institutional Review Boards/Ethic Committees (IRBs/IEs) per local IRB/IEC requirements.

7.3 Definitions

An **adverse event** is any untoward medical occurrence in humans, whether or not considered treatment- or procedure-related, which occurs during the conduct of a clinical trial. Any change in clinical status, routine labs, ophthalmological assessments etc., that is considered clinically significant by the Study Investigator or designee and requires intervention is considered an AE. Medical conditions or diseases present before a participant starts study treatment are only considered adverse events if they worsen after the participant starts study treatment (temporal association).

Suspected adverse reaction (Related Adverse Event) is any adverse event for which there is a reasonable possibility that the treatment caused the adverse event. A reasonable possibility implies that there is evidence that the treatment caused the event.

Serious Adverse Events

A serious adverse event (SAE) as determined by the Investigator or the Sponsor is any event that results in any of the following outcomes:

1. Death
2. Life-threatening AE (Life-threatening means that the study participant was, in the opinion of the Investigator or Sponsor, at immediate risk of death from the event as it occurred.)
3. Persistent or significant incapacity or substantial disruption of the ability to conduct normal life functions.
4. Inpatient hospitalization or prolongation of existing hospitalization.
5. Congenital abnormality or birth defect.
6. Important medical event that may not result in one of the above outcomes, but may jeopardize the health of the study participant or require medical or surgical intervention to prevent one of the outcomes listed in the above definition of serious event.

Note that the term “serious” is not a measure of severity, but speaks to a very specific definition as noted in 1-6 above.

A hospitalization for an elective or cosmetic procedure, scheduled prior to enrollment or during the course of the study, unrelated to the medical condition under study, is excluded from this definition of a serious adverse event.

Unexpected Adverse Event

An unexpected adverse event is an event where the specificity or severity of which is not consistent with the current approved product labeling (package insert) for the test article or the Investigator's Brochure. This includes an increase in the frequency or severity of a previously reported adverse event that is significantly above the rates known from previous experience with the test article.

Guidelines for Determining when Changes in Pre-Existing Conditions are Considered Adverse Events

Adverse events include illnesses with onset during the study or exacerbations of pre-existing illnesses. Exacerbation of pre-existing illness is defined as a clinically relevant increase in the severity of the illness as compared to the start of the study and should be considered when a participant requires new or additional treatment for that illness. Investigators should use the following guidelines to assess when an adverse event needs to be reported for a condition which results in a change to an ongoing medication and/or addition of a new medication:

- Addition of a new medication and/or change in ongoing medication due to an untoward (unfavorable and unintended) change in a participant's medical health for a disease/condition documented as ongoing at baseline.
- Addition of a new medication due to an untoward (unfavorable and unintended) change in a participant's medical health for a disease/condition not present at baseline.

Guidelines for Assessing Intensity of an Adverse Event

The Investigator should use the following definitions when assessing Intensity of an Adverse Event:

- **MILD:** Transient (< 48 hours) or mild discomforts, no or minimal medical therapy or intervention required, hospitalization not necessary, no or little limitation in normal activities.

- MODERATE: Mild to moderate limitation in activity, some assistance may be needed; possibly none but usually minimal intervention/therapy required; hospitalization possible.
- SEVERE: Marked limitation in activity, some assistance usually required; medical intervention/therapy required; hospitalization possible or likely.
- LIFE THREATENING: Extreme limitation in activity, significant and immediate assistance required; significant medical/therapy intervention required to prevent loss of life; hospitalization, emergency treatment or hospice care probable.
- FATAL: Death

Guidelines for Determining Causality of an Adverse Event

The Investigator will answer the following question when assessing causality of an adverse event to study treatment: "Is there a reasonable possibility that the treatment caused the event?" A reasonable possibility implies there is evidence that the specific event was caused by the study treatment. An affirmative answer designates the event as a suspected adverse reaction, and the AE is therefore considered "related." If the answer is no, then the AE is considered "unrelated." For every related adverse event, the Investigator will determine the causality in relation to the surgical procedure - those related to the device itself, and the CNTF.

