In 1982, Gass et al. published the seminal paper on macular telangiectasis (then called juxtafoveal or parafoveal telangiectasia). In further work, Gass et al. (Gass 1987 and Gass 1993) subdivided macular telangiectasia into three groups: Type 1: the telangiectasia is usually unilateral and associated with dilated retinal capillaries, leakage on fluorescein angiography and retinal thickening in mostly male patients. Type 2: Macular Telangiectasia (MacTel), leakage occurs during fluorescein angiography with manifest retinal capillary dilatation but without retinal thickening, and Type 3: 3 Macular Telangiectasia, capillary occlusion is suspected to cause telangiectasia. Mac Tel Type 2, the most common form of macular telangiectasia, is the disease evaluated in this study. This condition is typically diagnosed in the fifth or sixth decade of life in both sexes. This disorder is characterized by minimal exudation, superficial retinal crystalline deposits, retinal opacification and right-angle venules. As the disease progresses, intraretinal pigment plaques and intraretinal/subretinal neovascularization may develop.

In 2005, a prospective natural history study was initiated to define the clinical aspects of macular telangiectasia type 2 and to evaluate its progression. Several new features have now been described that alter our concept of the disorder's pathogenesis. One of the earliest signs is

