7.9 Reporting SAEs to the DSMC

The Coordinating Center will provide the DSMC with safety reports submitted to FDA/regulatory authorities as well as data on all SAEs on an ongoing basis.

The Investigator will ensure the timely dissemination of all AE information, including expedited reports and DSMC safety reviews, to the IRB and IEC in accordance with applicable local regulations and guidelines.

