1. Dilating drops or anesthetic drops may sting. They can cause an allergic reaction, or if contaminated, can cause an infection, but neither of these problems is very likely to occur.
2. Dilating drops can also cause a sudden increase of pressure (acute glaucoma) in eyes that are already predisposed to develop this condition. There is little risk of glaucoma being triggered in this way, but if it is, treatment is available.
3. In rare instances, the cornea may be abraded during measurement of intra-ocular pressure or use of a contact lens (used for examination purpose only and not a contact lens used to correct a participants' refractive error).

There are risks to the procedures required for participants in this study.

Optical Coherence Tomography is an FDA-approved imaging technique, which is not associated with any adverse events.

Fundus photography and autofluorescence are not associated with any adverse events, although some participants may experience mild discomfort due to the bright lights.

There are also risks associated with the operations performed during the NTMT-01 and NTMT-02 surgical visit to implant the device and/or perform the sham procedure. These risks will remain in the extension protocol in case any new procedure related adverse experiences are recorded. In general, the risks of intraocular surgery are very small. Some side effects could occur locally in the eye and could affect the participant's vision. There may be pain or infection, a small amount of bleeding, miosis, retinal detachment, cataract, vitritis and/or mild astigmatism.

In many cases, topical antibiotics and topical steroids can treat minor degrees of inflammation or infection. More serious infection or inflammation may require further surgery on the eye, likely with removal of the implant. The sham procedure of subconjunctival injection of lidocaine and inserting a final suture in the conjunctiva may be accompanied by subconjunctival bleeding, pain or infection which all can be readily treated without any functional changes or any other permanent structural changes.

A possible complication of the explant surgery, if necessary, to remove the NT-501 device is a retinal detachment. The probability of retinal detachment in the normal population is less than 1%. These other side effects are also possible (a probability of less than 1%):

- Bleeding in the eye
- Cataract
- Infection
- Inflammation inside the eye

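### The SAE exclusion for elective admissions in section 7.3 tests relation to MacTel but not to the surgery, implant or CNTF, so a treatment-related elective admission does not count as serious under the hospitalisation criterion

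*Combined protocol and SAP*

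**What the plan says.** Section 7.3 lists six criteria for an SAE, to be determined by the Investigator or the Sponsor. Criterion 4 is "Inpatient hospitalization or prolongation of existing hospitalization". Criterion 6 is a judgement category that opens: "Important medical event that may not result in one of the above outcomes, but may jeopardize the health of the study participant".

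After the list comes an exclusion. Its subject is "A hospitalization for an elective or cosmetic procedure", and it applies to such an admission when "scheduled prior to enrollment or during the course of the study, unrelated to the medical condition under study, is excluded from this definition".

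Section 2 identifies the condition: "Mac Tel Type 2, the most common form of macular telangiectasia, is the disease evaluated in this study". Section 10, on the risks of the implant operation, says: "There may be pain or infection, a small amount of bleeding, miosis, retinal detachment, cataract, vitritis and/or mild astigmatism". It names cataract again as a possible effect of explant surgery. Section 7.9 sends the Data and Safety Monitoring Committee (DSMC) the safety reports submitted to regulators, "as well as data on all SAEs on an ongoing basis".

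**The concern.** Leaving out admissions that were already arranged when the participant joined is ordinary practice and is not the difficulty. Two features of the clause go further.

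- **Timing.** It also covers procedures first scheduled while the participant is on study, with no exception for a condition that is new or has worsened.
- **Relatedness.** It asks whether the admission is related to the disease. It does not ask whether the admission is related to the treatment.

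Together they allow an on-study elective admission for a complication of the implant or its surgery to fall outside criterion 4 because the complication is not MacTel. Long-term safety is a stated objective (section 4), and section 8.4 plans descriptive tabulation with no formal testing, so the classification of each event passes directly into the reported result.

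**Working it through.** No arithmetic applies and the plan gives no figure to reproduce. The check is to read the clause against the rest of the protocol and apply it to one case.

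**What the protocol treats as related**

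- Section 7.3, causality guidelines: the question is whether the treatment caused the event. For related events, the investigator then attributes it to the procedure, the device or CNTF.
- Section 6.1.3: a group of ocular events is described as distinct from the usual course of MacTel and potentially related to surgery, implant or CNTF. Sectorial lens opacification is one of them.
- Section 10: the surgical risks include "miosis, retinal detachment, cataract, vitritis and/or mild astigmatism".
- Section 7.3, SAE exclusion: the only relation tested is to the medical condition under study.

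The exclusion is the one place where relation to the disease stands in for relation to treatment. Sections 6.1.3 and 10 show that the protocol itself regards the two as different. No other section narrows the clause.

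**Applying the clause to an elective inpatient cataract admission, scheduled on study, in an implanted eye**

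1. Is it an inpatient hospitalisation? Yes, by assumption, so criterion 4 would be met.
2. Is it elective? Yes, by assumption.
3. Was it scheduled before enrolment or during the study? Yes, during the study.
4. Is it unrelated to MacTel? Yes, on the protocol's own separation of such events from the disease.
5. Result: it is excluded. The investigator's judgement that the cataract is related to the implant or surgery does not enter at any step.

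**What SAE status changes**

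| Step | Serious | Not serious |
|---|---|---|
| Data entry (7.2) | within 24 hours | within 5 business days |
| Notice to Coordinating Center and Sponsor (7.4, 7.7) | within 24 hours | no 24-hour requirement |
| Expedited regulatory report (7.8) | if also unexpected and related | not available |
| Ongoing SAE data to the DSMC (7.9) | yes | not through this route |
| SAE summaries (8.5) | yes | no |
| AE summaries, including those related to implant or surgery (8.5) | yes | yes |
| Safety-outcome summary, if on the 6.1.3 list (8.4) | yes | yes |

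The admission itself no longer places the event in the middle column. Another criterion still can.

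**The case against.** The strongest reply is that little is lost. Every AE is documented and entered whatever its severity or attribution (7.2). The investigator must report it promptly with severity and causality (7.4). A medical monitor reviews safety information generally (7.11). Sectorial lens opacification is summarised as a safety outcome whether or not it is serious (6.1.3, 8.4). Criteria 1 to 3, 5 and 6 remain, and the Sponsor as well as the Investigator may classify an event as serious. Cataract surgery may not involve an inpatient stay, in which case criterion 4 is not met and the exclusion has no effect. The Safety Plan (7.1) is not available here and might clarify the point. All of this stands. It limits the consequence but does not repair the wording.

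A reader might infer more than the documents support:

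- **That any planned surgery for a new illness, such as a newly found tumour, is excluded.** The clause says elective or cosmetic, not planned, and does not define elective. Tumour surgery is scheduled but not plainly elective in that sense, and it is an obvious candidate for criterion 6. Emergency admissions are untouched.
- **That an excluded event reaches none of the safety channels.** It remains an AE, can be an SAE by another route, and is summarised under 8.5.
- **That the clause overrides all six criteria.** A site could read it so, because it speaks of the definition as a whole. The more natural reading is that it removes the hospitalisation as a trigger.
- **That the number of missed events can be calculated.** With all 73 participants (7 + 66) followed for the 3 years from Visit 1 to Visit 4, there are 73 × 3 = 219 participant-years. An assumed 2 to 5 admissions per 100 participant-years would give 219 × 0.02 = 4.4 to 219 × 0.05 = 11.0. The rate has no basis in the documents and covers admissions for any new condition. The product also needs full enrolment and retention, every admission to be elective, and no capture under another criterion. It does not measure treatment-related events.

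**Conclusion.** The point holds as one about wording. Read literally, section 7.3 takes an elective inpatient admission for a treatment-related, non-MacTel event out of criterion 4, including when the procedure is first scheduled on study and the investigator calls the event related. The loss is the automatic trigger for 24-hour reporting, the ongoing SAE feed to the DSMC, possible expedited reporting and entry in the SAE tables. AE capture and the efficacy analyses are unaffected.

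The size cannot be estimated, because the documents give neither an admission rate nor the share of such procedures done as inpatient stays. It may be small. The conclusion assumes that the condition under study means MacTel, as section 2 indicates, and that the Safety Plan does not already narrow the clause. Given the safety objective and the low cost of repair, the change should be made.

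**What to change.** In section 7.3, and in the Safety Plan if it repeats the clause, restrict the exclusion to a hospitalisation for an elective or cosmetic procedure that meets all three conditions:

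1. it was planned before extension consent;
2. it is for a condition that has not worsened since that consent;
3. it is not potentially related to the surgical procedure, the NT-501 device or CNTF.

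This removes the reference to procedures scheduled during the study and replaces the test against the condition under study. If the sponsor prefers to keep the present timing, the minimum change is to add the third condition.

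The cost is one sentence and a few additional SAE reports. No visit, treatment or analysis method changes.

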7.4 Obligations of Investigators

The Investigator is obligated to promptly report all adverse events. When submitting adverse event information, the Investigator may not delegate to someone other than a listed study physician the responsibility for reviewing the accuracy of the contents of an adverse event report. When reporting an adverse event, the Investigator must assign a severity grade to each event and also declare an opinion on the causality of the event relative to the study test article or procedure.

For any serious adverse event, the Coordinating Center and Sponsor must be notified ***within 24 hours*** of when the Investigator first learns of the occurrence of the event. Adequate information must be collected with supporting documentation to complete the standard electronic form set.

If the participant reaches the final scheduled follow-up visit, any new adverse events, as well as follow-up information for ongoing adverse events, must be recorded. For participants who

withdraw prematurely, adverse events should be followed until 30 days after last study visit. In any case, every attempt must be made by the Investigator to follow serious adverse events that are not resolved or medically stable within 30 days of the last study visit until they become resolved or medically stable.

7.5 Terminology for Adverse Event Descriptions

When reporting an adverse event, the event description should use the best matching terminology describing the event as found in the “Common Terminology Criteria for Adverse Events” (CTCAE, v 4.0). If an available CTCAE term fits the event well, no additional descriptors may be needed. However, any necessary descriptions should be used in order to clarify the event or to place it in an appropriate context. If an appropriate term matching the adverse event cannot be found in the CTCAE, the adverse event description should include a diagnosis, sign or symptom with additional information to facilitate subsequent categorization into MedDRA coding terms. Each reported event will be a single term or concept.

7.6 Reporting of Pregnancy

Pregnancy, in and of itself, is not regarded as an adverse event. A confirmed pregnancy in a participant (by urine or blood test) should be reported to the Coordinating Sponsor as soon as the Investigator has been made aware of the pregnancy. The decision on whether to remove the implant and terminate the participant from the study will be made by the Investigator and the participant following consultation with the Sponsor. The Investigator will use his/her expert judgment, based on an assessment of the potential benefit/risk to the participant, to determine if it is in the participant’s best interest to continue participation in the study.

A pregnancy in the partner of a participant should also be reported to the Investigator who will in turn notify the Coordinating Center as soon as possible.

The pregnancy should be followed until birth. The outcome of all such pregnancies (i.e., spontaneous miscarriage, elective termination, normal birth or congenital abnormality) must be documented and followed-up on a form that will be provided by the Coordinating Center. The pregnancy will be followed to term and the outcome, including any premature termination, must be reported to the Coordinating Center. All live births must be followed for a minimum of 30 days or to the first well-baby visit. All reports of congenital abnormalities/birth defects and spontaneous abortions/m miscarriages should be reported as an SAE for this study.

Elective abortion procedures, without complications, should not be considered as adverse events.

